## Section II. Research Plan and Design

#### A. Study Design Overview Figure 1. Study Design Screen individuals for eligibility After meeting study inclusion criteria, randomize individuals into Tx1, Tx2, or Tx3 Tx2 Tx3 Intervention (Tx1) **DPP** plus **DPP Only Usual Care** Breastfeeding (N=20) (N=20) (N=20) Ρ DPP - 16 sessions: Core Regular prenatal care DPP - 16 sessions: R R provided by physician curriculum (Phase I) Core curriculum (Phase I) E Е **Breastfeeding Education** N Ν 2-hour curriculum Α Α (between weeks 20 - 24) т т Breastfeeding Booster Α Α Session 1-hour curriculum L L (between weeks 28 - 32) Р At delivery – in-hospital At delivery - in-hospital At delivery - in-hospital 0 breastfeeding support breastfeeding support breastfeeding support s DPP - 15 sessions: Post-DPP - 15 sessions: Т core curriculum (Phase II) Post-core curriculum N (Phase II) Α **Breastfeeding** т Т Assessment (at five Α Α separate time points)

This is a three-arm pilot randomized controlled trial (RCT) to implement as well as determine the feasibility and efficacy of an intervention that is based on the Diabetes Prevention Program and includes intensive breastfeeding counseling and support among a cohort of overweight and obese pregnant women. Upon meeting eligibility criteria, participants will be randomly assigned to the DPP plus breastfeeding (intervention, Tx1), DPP Only (Tx2), or Usual Care (Tx3), and will be followed during pregnancy through 6 months postpartum. Participants in Tx1 will receive the DPP and targeted breastfeeding support during pregnancy through 6 months postpartum. Participants in Tx2 will receive the DPP only. Participants in

Tx3 will receive care as usual. Usual care is described as obstetrical care that women with normal BMI receive and that is provided by the same provider ([name]).

At recruitment and at study closure, participants will complete four survey instruments; each of which assesses women's knowledge of physical activity, nutrition, and breastfeeding (see appendices 1 through 4). Also, postpartum women will complete the Edinburgh Postnatal Depression Scale (EPDS, see appendix 5) and a study coordinator will assess postpartum women's breastfeeding experience with the Bristol Breastfeeding Assessment Tool (BBAT, see

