### D. Subject Selection Criteria and Recruitment

We will recruit pregnant patients from two obstetrical clinics: one clinic at Via Christi Hospitals Wichita, Inc. (VCH), a regional hospital in Wichita, and another clinic at Kearny County Hospital, a full-service rural hospital located in Lakin, southwest Kansas. [name], maternal fetal medicine specialist, sees pregnant women at this location, and he and his staff will actively assist with patient recruitment. During the first prenatal appointment, [name] will screen potential participants for inclusion criteria, and if he believes a participant meets inclusion criteria (see Table 1), then he will familiarize a potential participant with the study's purpose. If the potential participant is interested in the study, then he will give her a study brochure and a hard copy of the consent form. Prior to using this study brochure, the brochure will be reviewed and approved by the IRB at Via Christi Hospitals Wichita, Inc. By providing the potential

participant with a copy of the consent form, this will serve as the verbal consent script. [name] will also provide the potential participant's name and phone number to [name] and her research coordinator. After receiving a potential participant's name and phone number from [name], the research coordinator will follow up with a phone call to determine if the potential participant again meets study inclusion criteria, and if she does, the coordinator will screen if the potential participant meets study exclusion criteria during the same phone call (see Table 1). Before the research coordinator screens for inclusion and exclusion criteria, during this same phone call, verbal consent will be obtained between the participant and the research coordinator, using the consent form as the verbal consent script, and then written e-consent will be obtained via REDCap at the orientation session. Once the participant is enrolled in the study and over the course of her pregnancy develops one of the conditions mentioned under Exclusion (Table 1), then this will be reported to the Data and Safety Officer. It will then be decided in consultation with [name] if the participant will be able to continue participating in the study or if she will need to be dismissed.

Table 1. Enrollment Criteria

Inclusion
1. Pregnant
2. In 1st trimester or early in 2nd trimester
2. BMI ≥ 25 and < 35
3. At least 18 years old or older
Be able to understand English
5. Must have a cell phone

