We will employ a "rolling" recruitment period of 9 months, meaning that each participant may be at different completion stages. During their first face-to-face orientation session, participants will receive access to the secure, private group on Facebook. They will be asked to complete each Phase I module on their own time, starting at week 19 of pregnancy. To supplement their self-study of the curriculum, on a weekly basis, the research coordinator will follow up with each study participant via phone to check on progress. If participants do not make adequate progress, then the coordinator will assess how much extra time the participant needs to complete a module, and will work with her face-to-face via Skype, FaceTime or Zoom if needed. Participants will complete Phase I by week 33 of pregnancy.

Phase II consists of a total of 15 sessions that will be completed after delivery (see Table 2). Two of the Phase II DPP sessions (sessions #4 and #5 respectively) have been modified with the Cooking Matters curriculum that (1) emphasizes planning/preparing for healthy, low-cost meals and (2) encourages mothers to make smart choices when food shopping. Each of the fifteen (15) sessions/modules of Phase II will be pre-recorded and archived on the same secure, private group on Facebook mentioned above. Only Tx1 and Tx2 participants, [name] and the research coordinator will have access to this Facebook group.

Participants will re-engage into the DPP with another face-to-face orientation session conducted by [name] at week 6 postpartum. The same session completion format and procedure for inadequate progress will be followed as during pregnancy. Participants will complete Phase II by week 20 postpartum. An 80% completion rate of each phase is considered successful completion of the intervention.

Table 2. Timetable - Diabetes Prevention Program Sessions

Prenatal (Core Curriculum)	Postnatal (Post-core Curriculum)				
	Week of		Week of		
DPP Sessions - Phase I	Pregnancy	DPP Sessions - Phase II	Postpartum		
1 - Orientation - Welcome!	18	1 - Orientation - Welcome Back!	6		
2 - Cooking Matters (CM): Set a Healthy Example	19	2 - Fats: Saturated, Unsaturated, & Trans-Fats	7		
3 - Eating Less Fat and Fewer Calories	20	3 - Food Preparation & Recipe Modification	8		
4 - CM: Choosing Fruits, Vege's, Whole Grains	21	4 - Taking It One Meal at a Time, CM: Planning	9		
5 - Move Those Muscles	22	5 - Variety and Balance, CM: Shopping	10		

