Sample Size and Randomization. The primary outcomes of interest are: (1) postpartum weight loss; (2) HbA1c and mean arterial blood pressure; and (3) breastfeeding duration. A total of 60 participants (20 per study arm) will be recruited. The results from this pilot study will be used in sample size estimation for a future study that is sufficiently powered to detect a clinically meaningful effect size. Due to the nature of this project being a feasibility study, the sample size in the proposed study is not based on providing adequate power to detect a clinically meaningful effect size across the three study arms. Block randomization with block size of 5 participants will be employed. A sequence of 12 random integers will be generated using a computer algorithm. The first 4 integers of the sequence will be assigned to the DPP plus breastfeeding arm; the next 4 integers will be assigned to the DPP only arm; and the last 4 will be assigned to the usual care arm. Blocks will be assigned to arms in the increasing order of sequence of integers generated.

**Statistical Analysis.** For baseline data characteristics, descriptive statistics will be reported as mean and standard deviation for continuous variables and as count and percentage for categorical variables. Depending on the distribution of the continuous variables, the Kruskal-Wallis test or ANOVA will be used to test for differences in continuous variables across the three arms. Chi-

Square test of independence (or Fishers exact test if 25% of cells have counts less than 5) will be used to assess the association between categorical variables and the three arms. The analysis will be based on "intention-to-treat" principle. A two-sided alpha level of 0.05 will be used to determine statistical significance. A 95% confidence interval will also be reported.

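### Read literally, the randomisation rule gives each block of five women to a single arm; this conflicts with individual randomisation and could make most allocations predictable

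*Combined protocol and SAP*

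**What the plan says.** The rule is in Section III, under Sample Size and Randomization. It begins "Block randomization with block size of 5 participants will be employed" and continues "A sequence of 12 random integers will be generated using a computer algorithm". Four integers go to DPP plus breastfeeding, four to DPP only and four to usual care. It ends "Blocks will be assigned to arms in the increasing order of sequence of integers generated". The same paragraph gives 60 participants, 20 per arm.

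Section II.A describes a different unit. Figure 1 reads "After meeting study inclusion criteria, randomize individuals into Tx1, Tx2, or Tx3", and the text below it says "Upon meeting eligibility criteria, participants will be randomly assigned to the DPP plus breastfeeding". Sections IV.A.a and IV.C add only that a computer does the randomising.

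Three other parts of the plan bear on the point:
- **Enrolment.** It is rolling: Section II.F & G describes a "recruitment period of 9 months, meaning that each participant may be at different completion stages".
- **Staff roles.** After the specialist's first screen, Section II.D says "the research coordinator will follow up with a phone call to determine if the potential participant again meets study inclusion criteria", and the coordinator then applies the exclusions. Under Section II.F & G the coordinator also helps to administer the DPP, makes the weekly progress calls and makes the breastfeeding calls that only Tx1 receives.
- **Numbers.** Sections I.B, II.A (Figure 1), III and IV.A.a work with 60 women. Sections II.C and II.D plan to randomise 72, that is 24 per arm and 12 per arm at each site.

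**The concern.** Permuted blocks normally contain every arm in equal number, in random order. Here the thing assigned to an arm is the block itself, so the arm would change at most once every five women. Whoever sees the first woman's arm would then know the next four. Concealing the list would not prevent this, because the information lies in allocations already made, and the arms differ openly.

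The coordinator both sees arms and applies exclusions. Some of these call for judgement, such as whether a woman could finish the programme or is willing to monitor herself. If the next arm is foreseeable, such judgements can lean on it without intent. The resulting selection bias would enter the Aim 1 to 3 comparisons, and intention-to-treat analysis and covariate adjustment do not reliably remove it. It would also carry forward, since "The results from this pilot study will be used in sample size estimation for a future study".

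**Working it through.** **Inputs.** Block size 5, 12 integers, 4 per arm, total 60 and 20 per arm (Section III); 72 to be randomised, 24 per arm (Sections II.C and II.D).

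**1. Reproduce the plan's totals.** With one integer per block, 12 × 5 = 60 women and 4 × 5 = 20 per arm. Both match. The match does not settle the reading, because five permuted blocks of twelve with four per arm give the same totals: 5 × 12 = 60 and 5 × 4 = 20.

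**2. Can a block of five be balanced?** 5/3 = 1.67, so no equal split over three arms exists.

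**3. Allocations fixed under the literal reading, with blocks filled in order of entry.**
- Women after the first in each block: 12 × (5 − 1) = 48, and 48/60 = 80%.
- The first woman of a block is also fixed once only one arm has blocks left. The expected number of such blocks is 1 + 3/11 + (3/11)(2/10) + (3/11)(2/10)(1/9) = 1.33.
- The mean number fixed is 48 + 1.33 = 49.3 of 60. The range is 49 to 52, because between one and four final blocks can be forced.
- If the list were split by site, with two blocks per arm per site, the 48 would be unchanged: 2 sites × 6 blocks × 4 = 48.

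**4. Accuracy of an informed guesser.** The guesser knows the scheme and the past allocations and always names the arm with most places left. Let E(a, b, c) be the expected number of correct guesses with a, b and c places left and n = a + b + c. Then E = max(a, b, c)/n + the sum over arms of (places left in that arm / n) × E after removing one place from that arm.
- Literal rule: E(4,4,4) = 6.144 for the 12 first women. (48 + 6.144)/60 = 54.1/60 = 90%.
- Permuted blocks of 3: E(1,1,1) = 1/3 + 1/2 + 1 = 1.833. 1.833/3 = 61%.
- Permuted blocks of 6: E(2,2,2) = 3.367. 3.367/6 = 56%. Fixed allocations: 10 × (1 + 1/5) = 12 of 60.
- Permuted blocks of 12: E(4,4,4) = 6.144. 6.144/12 = 51%. Fixed allocations: 5 × 1.33 = 6.7 of 60.

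**5. Does the list cover the women?** Twelve blocks of five give 60 places. With 72 randomised, 72 − 60 = 12 women have no place, and 24/5 = 4.8 blocks per arm is not a whole number.

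**The case against.** The strongest objection is that the whole-block reading may not be what was meant. Drawing twelve random integers, labelling four for each arm and sorting them is a usual way to make one permuted block of twelve. On that reading, five is the number of blocks, misworded as the block size. It would agree with Figure 1, it gives the same 60 and 20, and blocks of twelve would also fit 72 (six blocks). Predictability would then be ordinary. It is the less literal reading, since both the sentence on block size and the sentence assigning blocks to arms would have to be wrong. But the totals cannot exclude it, and the 80% and 90% figures hold only if the text means what it says.

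The conditions also matter. Section III does not say that a block is five consecutive entrants; that is inferred from rolling enrolment. A guesser needs to know or infer the block boundaries and to see earlier arms, across both sites if there is one list. The specialist who screens first has no clear delivery role, and most exclusions are factual. The coordinator's second screen on the few judgement-based items remains a real route.

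A reader might infer that allocation is not concealed. The documents do not support that: the available text describes no concealment step, but the part of the protocol between Sections II.D and II.F & G was not available for review. Absent concealment is therefore not used as evidence here.

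Finally, Section III calls this a feasibility study without adequate power. That limits the inferential harm but does not remove it, because efficacy is still tested at two-sided 0.05 and the estimates will inform the next trial.

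**Conclusion.** The point stands in conditional form. As written, the rule assigns whole blocks of five to one arm, contradicts the individual randomisation in Section II.A and cannot balance three arms within a block. If blocks follow order of entry and earlier arms are visible to screening staff, at least 48 of 60 allocations are determined and informed guessing succeeds about 90% of the time, against 56% for known permuted blocks of six. If five permuted blocks of twelve were intended, the figure is about 51% and the defect is one of wording. Under either reading the sentences cannot stand.

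Two stronger conclusions are tempting and are not supported. The first is that selection bias will occur: the documents show a route for it, not its presence or size. The second is that the planned standard errors are too small because only twelve units are randomised. That is possible if outcomes drift over calendar time, but no document gives a within-block correlation or a drift, so the effect is unquantified and adds nothing to the severity.

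The change is needed before the first randomisation, because bias that enters at allocation cannot be reliably repaired in the analysis.

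**What to change.** Replace the block sentences in Section III with a rule stating that:
- women are individually randomised 1:1:1, with arms permuted within blocks whose size is a multiple of three;
- the list is stratified by site, because Sections II.C and II.D plan equal numbers per arm at each site;
- the block size is held in a restricted document, not printed in the protocol;
- an automated system, or a list holder with no part in screening or delivery, releases each allocation only after eligibility and written e-consent are recorded. Any concealment step already in the protocol should be kept.

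Add site as a covariate in the Aim 1 to 3 models.

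Size the list to the number to be randomised, and reconcile the 60 in Sections I.B, II.A, III and IV.A.a with the 72 in Sections II.C and II.D. Suitable block sizes exist for either total; six, for example, gives 36/6 = 6 or 30/6 = 5 blocks per site.

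The cost is a new computer-generated list, a small list-holding task that the available text assigns to no one, one model degree of freedom for site, and one amendment approved before implementation (Section IV.I; Section IV.A.a names three institutions). The amendment must also fix when allocation is released. E-consent is signed just before orientation (Section IV.B.a) and orientation opens the DPP Facebook group (Section II.F & G), so release has to fall between the two. No participants are added.

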### Section I. Purpose, Background and Rationale

### A. Specific Aims and Hypotheses

In the proposed randomized controlled trial, we seek to determine the feasibility and efficacy of a combined breastfeeding, DPP-based program in a cohort of overweight/obese women to be followed during pregnancy through 6 months postpartum. Our trial will have three study arms: DPP plus breastfeeding (Tx1); DPP Only (Tx2); and Usual Care (Tx3). Specific aims are:

Aim 1: Test the efficacy of Tx1 to improve 6-month postpartum weight loss among women with a BMI  $\geq$  25. We will measure maternal height and weight at baseline; weight at delivery and 6 months postpartum.

Hypothesis 1: Women in Tx1 will have greater weight loss postpartum compared to women in Tx2 and Tx3.

Aim 2: Test the efficacy of Tx1 to improve 6-month postpartum mean blood glucose (HbA1c) and mean arterial blood pressure among women with a BMI  $\geq$  25. We will measure HbA1c and mean arterial blood pressure at baseline, delivery, and 6 months postpartum. Hypothesis 2: Women in Tx1 will have better HbA1c and mean arterial blood pressure postpartum compared to women in Tx2 and Tx3.

Aim 3: Test the efficacy of Tx1 to increase any breastfeeding through 6 months postpartum among women with a BMI  $\geq$  25. We will measure any breastfeeding continuance at week 1, 3, and 6 postpartum, and at 3 and 6 months.

Hypothesis 3: Women in Tx1 will breastfeed longer compared to women in Tx2 and Tx3.

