Aim 1: Test the efficacy of Tx1 to improve 6-month postpartum weight loss among women with a BMI  $\geq$  25. The outcome of interest is 6 month postpartum weight loss measured across the three arms. Weight will be measured at delivery, and at weeks 1, 3, and 6 postpartum and at 3 months (13 weeks) and 6 months (26 weeks) postpartum. The difference in postpartum weight (weight loss) between two consecutive time points will be computed. Thus, each participant has 5 postpartum weight loss values based on weight measurements at 6 different time points. We will use the generalized estimating equation approach to compare weight loss in the DPP plus breastfeeding arm (Tx1) with weight loss in the DPP only (Tx2) and usual care (Tx3) arms, as well as weight loss between Tx2 and Tx3. The working correlation matrix will be specified after assessing the data. The model will be adjusted for the effect of age, race/ethnicity, level of education, annual household income, family history of diabetes, baseline weight, pre-diabetes status, and parity.

Aim 2: Test the efficacy of Tx1 to improve 6-month postpartum mean blood glucose (HbA1c) and mean arterial blood pressure among women with a BMI  $\geq$  25. The outcome of interest is mean blood glucose (HbA1c) and mean arterial blood pressure ((systolic blood pressure +2 (diastolic blood pressure)/3)) measured at baseline, delivery, and at 6 months postpartum across the three arms. We will use a multiple linear regression approach to compare HbA1c in Tx1 with HbA1c in Tx2 and Tx3, as well as HbA1c between Tx2 and Tx3. The model will be adjusted for the effect of age, race/ethnicity, level of education, annual household income, family history of diabetes, pre-diabetes status, parity, and baseline weight. The difference in mean blood arterial pressure at 6 months postpartum will also be assessed using a separate multiple linear regression approach after adjusting for the same covariates listed previously.

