Aim 3: Test the efficacy of Tx1 to increase any breastfeeding through 6 months postpartum among women with a BMI  $\geq$  25. The outcome of interest is breastfeeding through 6 months postpartum; it will be measured at delivery, and at weeks 1, 3, and 6 postpartum and at 3 months (13 weeks) and 6 months (26 weeks) postpartum. The risk of stopping "6 month postpartum breastfeeding" in Tx1 relative to Tx2 and Tx3 will be estimated using Zou's modified Poisson regression approach. The outcome in Zou's modified Poisson regression is binary, and it does not take into account the time until which any breastfeeding was done before stopping. However, it provides an interpretation-friendly estimate of the probability of stopping "6 month postpartum breastfeeding." Additionally, the Cox Ph model will be used to compare the risk (hazard) of stopping breastfeeding across each study arm. Unlike Zou's modified Poisson approach, the Cox model takes into account the time of breastfeeding. Any participants who are lost to follow-up will be treated as censored events and participants who stop

breastfeeding during the follow-up are the events of interest. In addition, participants who performed any breastfeeding until 6 months will be treated as administratively censored events. The model will be adjusted for the same covariates listed above under Aims #1 and #2.

Missing data. Owing to the design of the study and non-transient nature of the study population, we anticipate few to none missing observations. Any missing observation that can be attributed to either attrition or nonresponse will be considered missing at random. Depending on the proportion of missingness, complete case analysis (less than 5% missing) or the multiple imputation method will be used to impute missing data. For longitudinal response (postpartum weight measurements), the last observation will be carried forward to impute the missing response. Results based on imputed data will be compared to findings from complete case analysis, to assess the effect of missingness on study findings.

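### Four unranked primary outcomes are tested by arm contrasts at 0.05 with no rule for when a hypothesis is supported; with no true effect, a significant result favouring Tx1 arises somewhere in about 13–17% of trials

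*Combined protocol and SAP*

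**What the plan says.** Under Sample Size and Randomization (Section III), "The primary outcomes of interest are: (1) postpartum weight loss; (2) HbA1c and mean arterial blood pressure; and (3) breastfeeding duration". The second item holds two variables, so there are four, and none is placed first. The same passage describes a feasibility study whose sample size does not rest on power. Under Statistical Analysis, "A two-sided alpha level of 0.05 will be used to determine statistical significance", and 95% confidence intervals are promised.

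The comparisons are then set out by aim:

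- **Weight loss:** Tx1 against Tx2, Tx1 against Tx3, "as well as weight loss between Tx2 and Tx3". That is three contrasts.
- **HbA1c:** the model is to "compare HbA1c in Tx1 with HbA1c in Tx2 and Tx3, as well as HbA1c between Tx2 and Tx3". Again three.
- **Mean arterial pressure:** "The difference in mean blood arterial pressure at 6 months postpartum will also be assessed using a separate multiple linear regression approach". No contrasts are listed.
- **Breastfeeding:** the risk of stopping "in Tx1 relative to Tx2 and Tx3 will be estimated using" modified Poisson regression (two contrasts). Then: "Additionally, the Cox Ph model will be used to compare the risk (hazard) of stopping breastfeeding across each study arm". Neither model is named as the lead.

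Section I.A words the hypotheses in the form "Women in Tx1 will have greater weight loss postpartum compared to women in Tx2 and Tx3". Hypothesis 2 also joins HbA1c and arterial pressure with *and*. Every aim is phrased as a test of efficacy. The text contains no multiplicity adjustment, testing order, gatekeeping step or success criterion.

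**The concern.** A rule for declaring significance without a rule for declaring a hypothesis supported leaves the second decision open until the data are seen. A reader could call Hypothesis 1 supported if Tx1 beats either comparator, or only if it beats both. Hypothesis 2 could rest on one variable or two, and Hypothesis 3 on either of two models.

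Section III says the results will be used to size a later trial, and Section IV.D ties the knowledge gained to a larger grant application. In a small trial, an effect singled out because it crossed 0.05 tends to be an overestimate, and that estimate could be carried forward.

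**Working it through.** The documents give no familywise error rate, so there is no figure of theirs to reproduce. The check asks how often significant results appear when no arm differs.

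**Inputs from the documents.** Two-sided 0.05 per test; three equal arms; 20 per arm completing or 24 randomized; four primary variables.

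**Assumed.** Correlation between outcomes, which the documents do not give: 0 to 0.5, with 0.7 as a stress value. Outcomes are treated as normal and compared by unadjusted t tests. Breastfeeding is represented by one such statistic.

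**Step 1: one outcome, results favouring Tx1.** Each Tx1 contrast is significant in the favourable direction with probability 0.025. The two contrasts share the Tx1 arm, so their test statistics correlate at 0.5, and the bivariate normal probability that both exceed 1.96 is 0.0046.

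- Tx1 better than both comparators: 0.0046, about 0.5%.
- Tx1 better than at least one: 0.025 + 0.025 − 0.0046 = 0.0454, about 4.5%.

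**Step 2: four outcomes, results favouring Tx1.** For independent outcomes:

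- at least one favourable contrast: 1 − (1 − 0.0454)^4 = 0.170;
- both comparators beaten on at least one outcome: 1 − (1 − 0.0046)^4 = 0.018.

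Simulated t tests at 20 and 24 per arm agree. A favourable Tx1 contrast on some outcome occurs in about 17% (correlation 0), 15% (0.3) and 13–14% (0.5). Beating both comparators on some outcome stays under 2% throughout.

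**Step 3: Hypothesis 2 on its loosest reading.** Two outcomes, either comparator, independent: 1 − (1 − 0.0454)^2 = 0.089, about 9%.

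**Step 4: any contrast, either direction.** One outcome with three contrasts gives about 12.3%. Four independent outcomes give 1 − (1 − 0.123)^4 = 0.41. With correlation:

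| Correlation | Any of 12 contrasts significant |
|---|---|
| 0 | 41% |
| 0.3 | 38% |
| 0.5 | 34% |
| 0.7 | 29% |

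This count takes three contrasts for arterial pressure, which the plan does not list, and one Aim 3 model. Counting instead weight loss 3, HbA1c 3, arterial pressure 2, Cox 3 and modified Poisson 2, with the two Aim 3 statistics correlated at an assumed 0.8, gives 41.7% (correlation 0) to 35.8% (0.5).

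**Step 5: the second Aim 3 model.** A null simulation used 20 per arm, the background's 79% initiation and 29% still breastfeeding at 6 months, assumed rates in between, and a log-rank test in place of Cox. The two tests correlate at 0.92. Adding the two modified Poisson contrasts to the three log-rank contrasts raises the chance of a significant result from 12.7% to 14.1%. The second model adds little error. The gap is that neither is designated.

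**The case against.** The strongest reply is that this is a pilot. The plan disclaims power, says its results will inform a later sample size, and promises confidence intervals. No clinical or regulatory decision is described as resting on the p-values. That stands, and it lowers the severity. It does not remove the gap, because the aims are still framed as efficacy tests with a threshold for significance.

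A second reply is that the natural reading of "Women in Tx1 will have greater weight loss postpartum compared to women in Tx2 and Tx3" already requires Tx1 to beat both comparators, which keeps the error very low. That is a reasonable reading, but the plan does not state it, and it does not settle Hypothesis 2 or the choice of Aim 3 model.

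A reader might infer that the trial has a 34–41% chance of falsely supporting its hypotheses. The documents do not bear that out. That figure includes Tx2-against-Tx3 contrasts, which no hypothesis concerns, and results in which Tx1 does worse. It also takes three arterial-pressure contrasts that are not listed. Nor should the six modelled survey scores be counted as 18 further pairwise tests, since the plan assesses them across the arms without listing pairs. Finally, *co-primary* would be the wrong label: it normally means that all must succeed, and the plan says only that these are primary outcomes.

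**Conclusion.** The concern holds as a gap in the decision rule, at the level of something that should be fixed. The figure relevant to a false claim for Tx1 is about 13–17% across the four outcomes if any favourable contrast counts, and under 2% if both comparators must be beaten on the same outcome. The distance between the two comes from an interpretation the plan leaves open, compounded by pooling over unranked outcomes.

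Weight loss taken alone is not a problem: even the looser reading stays near 4.5% in the claimed direction. The 34–41% range (29% at correlation 0.7) is the chance of some significant pairwise result of any kind, and should be described only as that.

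All these figures rest on the assumed correlations and on tests that hold their nominal level. Estimating-equation and regression models with eight covariates at about 20 women per arm could shift them.

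**What to change.** In Section III, state that because the sample is not based on power, the efficacy comparisons are exploratory and will be reported as estimates with the 95% confidence intervals already promised, without significance claims.

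If a formal claim is kept for any hypothesis, name beforehand the outcome it rests on and require Tx1 to beat both Tx2 and Tx3 at two-sided 0.05. Which outcome to name is the investigators' choice, since nothing in the documents ranks one above another.

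For Hypothesis 3, which concerns how long women breastfeed, make the time-to-stopping model the lead analysis and the modified Poisson risk ratio supportive. The plan itself notes that the latter ignores time.

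The cost is a wording change, with no new data or participants. Fewer results can be called significant.
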